4.2 Outcome variables

Because of the exploratory nature of the trial and according to methodological guidance for exploratory trials, a distinction between primary and secondary endpoints is not made [23]. The presence of IAD is, however, with consideration of the study protocol considered as main outcome variable, i.e. primary outcome.

Variables marked with (day0) will be considered as baseline data. All outcome variables are measured in eight study visits in total (one baseline visit [Day0] and seven follow-up visits [Day2, Day4, ..., Day14]).

Characteristic	eCRF table	Variable name	Type	Scale	Comment/Analysis
IAD incidence	mnppid_skin				Main outcome Measured via occurrence of IAD at given visit (skin_0011)
IAD present?		skin_0011	cat	0-no 1-yes	n (%)
Location front		skin_0015	cat	0-no 1-yes	n (%)
Location back		skin_0016	cat	0-no 1-yes	n (%)
GLOBIAD category (front)		skin_0012	cat	1-1A 2-1B 3-2A 4-2B	n (%) (check skin_0015)
GLOBIAD category (back)		skin_0017	cat	1-1A 2-1B 3-2A 4-2B	n (%) (check skin_0016)
Erythema (visual)					Multi variable
"Redness?"		skin_0021		0-None 1-Pink 2-Red/bright red	main focus if available, else build variable based on 0026, 0027a and 0028a; (highest level counts) n (%)
n.a.		skin_0023		0-no 1-yes	Check if contradicts skin_0026, 0027a and 0028a
None		skin_0026		0-no 1-yes	
Pink		skin_0027a		0-no 1-yes	
Front		skin_0027b		0-no 1-yes	n (%)
Back		skin_0027c		0-no 1-yes	n (%)
Red/bright red		skin_0028a		0-no 1-yes	
Front		skin_0028b		0-no 1-yes	n (%)
Back		skin_0028c		0-no 1-yes	n (%)
Erythema level (1)		Func_0081 (day0) func_0141	Numeric	Arbitrary units (AU) from 0 (= no erythema) to 999 (= extreme erythema)	Mean (sd) check func_0082 func_0142, func_0143
Erythema level (2)		Func_0083 (day0) func_0144	Numeric	Arbitrary units (AU) from 0 (= no erythema) to 999 (= extreme erythema)	Mean (sd) check func_0084

Characteristic	eCRF table	Variable name	Type	Scale	Comment/Analysis
					func_0145, func_0146
Erythema level (total)			Numeric	Arbitrary units (AU) from 0 (= no erythema) to 999 (= extreme erythema)	Mean (sd) of (Erythema level 1 + Erythema level 2)/2
Erosion					
"Erosion present?"		skin_0041		0-no 1-yes	n (%)
Front		skin_0044		0-no 1-yes	n (%)
Back		skin_0045		0-no 1-yes	n (%)
Maceration					
"Maceration present?"		skin_0051		0-no 1-yes	n (%)
Front		skin_0054		0-no 1-yes	n (%)
Back		skin_0055		0-no 1-yes	n (%)
Local intolerances					
Have any local intolerances occurred since the last visit?		skin_0061		0-no 1-yes	n (%)
current condition		skin_0062		1-Homogeneous redness with scattered papules 2- Homogeneous redness and homogeneous infiltration 3- Homogeneous redness and infiltration with vesicles 4- Homogeneous redness and infiltration with coalescing vesicles	n (%)

Functional assessments					
Characteristic	eCRF table	Variable name	Type	Scale	Comment/Analysis
MMSE	mnppid_assessments (day0) mnppid_assessments1 (else)				Relevant for dementia and IAD related pain
MMSE-Score	mnppid_assessments	Func_0021	Numeric	Score; Range 0-30	Mean (sd)

Functional assessments					
Characteristic	eCRF table	Variable name	Type	Scale	Comment/Analysis
MMSE Score unknown	mnppid_assessments	Func_0022	cat	0-no 1-yes	
Has the subject a MMSE Score of 24 or higher?	mnppid_assessments1	Func_0090			Check func_0021
Cognitive Ability	mnppid_assessments	Func_0030		1-≥ 24 (Normal cognition; no dementia) 2-19 to 23 (Mild dementia) 3-10 to 18 (Moderate dementia) 4-9 and lower (Severe dementia)	N (%) Result of func_0021
Barthel Index Physical function	mnppid_assessments	Func_0041	Numeric	Score; Range 0-100	Mean (sd)
Barthel Index unknown	mnppid_assessments (day0)	Func_0042	cat	0-no 1-yes	
IAD related pain					Choice of Score depending on MMSE
IAD present?	mnppid_assessments (day0)	func_0057	cat	0-no 1-yes	Compare with skin_0011
NRS (numeric rating scale)	mnppid_assessments (day0) mnppid_assessments1 (else)	Func_0052 (day0) func_0101	Numeric	0 - 10 [numeric]	Mean (sd) if (MMSE Score ≥ 24) (check func_0051) (check func_0102 and 0103)
PAINAD-G	mnppid_assessments (day0) mnppid_assessments1 (else)	Func_0054 (day0) func_0111	Numeric	0 - 10 [numeric]	Mean (sd) if (MMSE Score < 24) (check func_0053) (check func_0112 and 0113)
No assessment	mnppid_assessments (day0)	Func_0055	cat	0-no 1-yes	
IAD related itch					
IAD-related itch reported by patient?	mnppid_assessments (day0) mnppid_assessments1 (else)	Func_0061 (day0) func_0121	cat	-2-No assessment -1- N.A. (no IAD present) 0-No 1-Yes	Func_0062 and func_0122 for missing analysis

Functional assessments					
Characteristic	eCRF table	Variable name	Type	Scale	Comment/Analysis
Patient satisfaction (of incontinence treatment)	mnppid_assessments (day0) mnppid_assessments1 (else)	Func_0071 (day0) func_0131	Numeric	0 - 10 [numeric]	Mean (sd) if (MMSE Score \geq 24) (check func_0053) NRS from 0 (= dissatisfied) to 10 (= very satisfied) (check func_0072 for missings) and func_0132,func_0133)

4.3 Secondary variables

The main clinical outcome is IAD incidence. All other outcome variables are considered secondary.

4.4 Efficacy

The main efficacy variable is the IAD cumulative incidence measured by IAD presence on each visit day (Day0, Day2, ..., Day14). Secondary efficacy variables are Erythema and Maceration level, IAD itch and pain level and patient satisfaction.

- IAD-related itch and pain level (numeric rating scale) are measured at each visit day (Day0, Day2, ..., Day14) if IAD is present and if MMSE \geq 24.
- IAD itch and pain level (PAINAD-G) are measured at each visit day (Day0, Day2, ..., Day14) if IAD is present and if MMSE < 24.
- Patient satisfaction is measured at each visit day (Day0, Day2, ..., Day14) if MMSE \geq 24
- Erythema and Maceration level are measured at each visit day (Day0, Day2, ..., Day14).

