Erosion	
 • Definition of erosion according to the latest International League of Dermatological Societies glossary of cutaneous lesions [27]: “Loss of either a portion of or the entire epidermis” 	Days 0, 2, 4, 6, 8, 10, 12, 14	
 • Presence of Erosion: (1) No; (2) Yes
Maceration	
 • Definition of maceration according to review article [28]: “(…) maceration (...) is the result of prolonged exposure (of the skin) to moisture and causes the skin to soften and breakdown so that the connective fibres can be teased apart and the skin often exhibits a white appearance.” 	Days 0, 2, 4, 6, 8, 10, 12, 14	
 • Presence of Maceration: (0) No; (1) Yes

Outcome Name	Device/Measurement instrument/Scale and metric	Time points	Response Options/Categories/ Range
IAD related pain	
 Numeric rating scale (NRS) from 0 (= no pain) to 10 (= worst possible pain) (see Fehler! Verweisquelle konnte nicht gefunden werden.) for patients/residents without cognitive impairment (according to Mini-Mental-State-Examination (MMSE) [29] with scores of 24 or higher) Means 	Days 0, 2, 4, 6, 8, 10, 12, 14	
 IAD related pain: 0 - 10 [numeric]
	
 Pain Assessment in Advanced Dementia (PAINAD-G) scale [30, 31] (see Fehler! Verweisquelle konnte nicht gefunden werden.) will be used for patients/residents with dementia (according to MMSE [29] scores of < 24; see Fehler! Verweisquelle konnte nicht gefunden werden.) Means 	Days 0, 2, 4, 6, 8, 10, 12, 14	
 IAD related pain: 0 - 10 [numeric]
Patient satisfaction	
 Definition according to [32]. NRS from 0 (= dissatisfied) to 10 (= very satisfied) (see Fehler! Verweisquelle konnte nicht gefunden werden.) for patients/residents with MMSE [29] scores of 24 or higher Means 	Days 0, 2, 4, 6, 8, 10, 12, 14	
 Patient satisfaction: 0 - 10 [numeric]
IAD related Itch	
 Patient reported IAD related itch 	Days 0, 2, 4, 6, 8, 10, 12, 14	
 Presence of IAD related itch (0) No (1) Yes

Outcome Name	Device/Measurement instrument/Scale and metric	Time points	Response Options/Categories/ Range

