2.7.3 RESIDENT/PATIENT REPORTED OUTCOME MEASURES

Participants are asked if IAD related itch is present or not. IAD related pain will be assessed with a numeric rating scale (NRS) from 0 (= no pain) to 10 (= worst possible pain) (**Fehler! Verweisquelle konnte nicht gefunden werden.**) for patients/residents without cognitive impairment (according to Mini-Mental-State-Examination (MMSE) [29] (**Fehler! Verweisquelle konnte nicht gefunden werden.**) with scores of 24 or higher). For patients/residents with dementia (according to MMSE [29] scores of < 24) the Pain Assessment in Advanced Dementia (PAINAD-G) [30, 31] scale will be used (**Fehler! Verweisquelle konnte nicht gefunden werden.**). Patient satisfaction is assessed by

NRS from 0 (= dissatisfied) to 10 (= very satisfied) (**Fehler! Verweisquelle konnte nicht gefunden werden.**) for patients/residents with MMSE [29] scores of 24 or higher. Definition according to [32].

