Physical function	
 Barthel – Index Score range: 0 to 100 Means 	Day 0	
 Item 1: Feeding (0; 5 or 10 points) Item 2: Bathing (0 or 5 points) Item 3: Personal toilet (0 or 5 points) Item 4: Dressing and undressing (0; 5 or 10 points) Item 5: Controlling bowels (0; 5 or 10 points) Item 6: Controlling bladder (0; 5 or 10 points) Item 7: Toilet use (0; 5 or 10 points) Item 8: Transfer (bed to chair and back) (0; 5; 10 or 15 points) Item 9: Standing up and Mobility (0; 5; 10 or 15 points) Item 10: Ascend and descend stairs (0; 5 or 10 points)
Diarrhoea	
 Interview by study assistant or obtained from medical records 	Day 0	
 Diarrhoea (0) No (1) Yes
Urinary tract infection	
 Interview by study assistant or obtained from medical records 	Day 0	
 Urinary tract infection (0) No (1) Yes

Demographic variables (age, sex, care level,), main medical diseases, medications and, if possible, Barthel-Index scores will be obtained from medical records by trained study assistants. Data regarding incontinence will be obtained from the medical records or if possible via interview of the participants or the responsible caregiver.

A possible cognitive impairment will be rated using the MMSE [29]. Only residents with a score of 24 or higher will receive the questionnaires regarding itch, pain and patient satisfaction. A functional assessment using the Barthel-Index will be conducted by study assistants, if this has not already been done by the nursing home. The Barthel-Index measures physical function related to the daily activities using ten items (e.g. washing and toilet use, eating and mobility or incontinence). Scores ranges from 0 (= very dependent) to 100 (= not dependent) [38].

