5.1 Missing values

In all analyses, missing values on either the outcome measures or on the covariates will be handled by using multiple imputation by chained equation (MICE) with $m = 30$ imputed datasets if MAR or MCAR assumption holds. To evaluate whether individual missings are MAR, MCAR or MNAR we will use information on reasons of missings or drop out (e.g. if patients drop out due to worsening of health status or not). In case of death, no imputation will be implemented for the time afterwards.

6 Sample size

Due to the exploratory nature of the trial, a formal sample size calculation is not applicable [23]. The trial has two subgroup strata (I) sex (male/female); (II) condition of the skin (no IAD vs. IAD Category 1A) and three treatment arms. Based on these conditions and following the recommendations for exploratory trials [36], a sample size of $n = 60$ participants per treatment group is considered feasible and sufficient to describe group differences. In order to compensate a possible loss-to-follow-up, $n = 70$ patients per group will be included.

7 Statistical analyses / methods

For all analyses, appropriate descriptive statistics (mean, standard deviation, median, interquartile range, absolute and relative frequencies) depending on the scale and distribution of the outcome variable for each time point will be presented. For relative frequencies of outcome variables, their cumulative incidences will be reported as well. Sensitivity analyses include per protocol analyses and complete case analyses in the ITT (without imputation).

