7.2 Analyses of endpoints

Because of the exploratory nature of the trial and according to methodological guidance for exploratory trials, a distinction between primary and secondary endpoints is not made [23]. Because the main aim is to prevent IAD, IAD incidence is likely to be considered as a primary outcome in a possible subsequent confirmatory trial and is therefore considered as primary efficacy variable.

For all outcomes, total group differences are reported by the corresponding effect size based on the statistical models as outlines below and corresponding 95% confidence intervals. Relevant timepoints will be Day 6 and Day14. Day0 reports will be presented as is.

The relevant blinded group comparisons are: A vs. B; A vs. C; B vs. C.

For cumulative incidence rates of IAD, Kaplan-Meier Curves will be presented with time ranging from inclusion to IAD onset, i.e. the first occurrence of IAD 2A or 2B. Censoring occurs if patients withdraw from the study before the onset of an IAD or if the study is terminated before IAD onset. Mixed effects Cox regression model (shared frailty model) will be carried out for group comparisons of incidence rates. The latter includes group allocation, sex, setting (nursery home, geriatric hospital ward) and time (continuous) as fixed effects and random intercepts for the ward and the patients. The resulting Hazard ratios for IAD will be presented. Potential non-linear time effects will be explored and modelled using fractional polynomials or splines.

Group differences for categorical, dichotomous responses are calculated by estimating group effects from either generalized linear mixed-effects models (binary logistic) - including particular baseline status (maceration, IAD-related itch), group allocation, sex, setting and time as fixed effects and random intercepts per ward and patients - or nonparametric analysis of longitudinal data depending on the distribution of the data. For the Erosion model, no baseline adjustment is considered due to its presence is an exclusion criterion.

List:

- Erosion (no/ yes)
- Maceration (no/ yes)
- IAD related itch (no/ yes) [only measured if IAD present]
- IAD-related pain (no/yes) [only measured if IAD present]

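### The documents disagree on whether itch is asked below MMSE 24, and the SAP's imputation rule does not except itch that was never asked

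*Combined protocol and SAP*

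**What the plan says.** Four places say who is asked about itch.

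- **Protocol 4.1.3** sets a cognitive threshold: "Only residents with a score of 24 or higher will receive the questionnaires regarding itch, pain and patient satisfaction".
- **Protocol 2.7.3** sets none: "Participants are asked if IAD related itch is present or not". The MMSE split in that section applies to pain and satisfaction only.
- **Protocol Table 2 (section 2.7)** defines the outcome as "Patient reported IAD related itch", yes or no at all eight visits. The pain and satisfaction rows carry an MMSE condition; the itch row does not.
- **SAP 4.4** has two lines, both requiring IAD to be present. For MMSE 24 or higher: "IAD-related itch and pain level (numeric rating scale) are measured at each visit day". For MMSE below 24: "IAD itch and pain level (PAINAD-G) are measured at each visit day".

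The SAP 4.2 variable table holds one itch item, "IAD-related itch reported by patient". It has separate codes for not assessed (-2) and for no IAD present (-1). No proxy or observational itch item is listed.

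SAP 7.2 lists the modelled outcome as "IAD related itch (no/ yes) [only measured if IAD present" and attaches no MMSE condition. In the same section, NRS pain and satisfaction are limited to MMSE 24 or higher.

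SAP 5.1 says: "In all analyses, missing values on either the outcome measures or on the covariates will be handled by using multiple imputation". This means chained equations with 30 imputed datasets, provided MAR or MCAR holds. SAP section 7 adds complete-case analysis as a sensitivity analysis.

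**The concern.** From these texts a reader cannot tell whether a participant with MMSE below 24 should have an itch value, or what the analysis does when there is none. The imputation rule makes this more than a drafting matter. It has no exception for values that were not collected by design, so a stratum with no observed itch could be filled with imputed itch.

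Whether the regime reduces itch is a named research question in protocol 1.2 and SAP 1.1.2. So is whether the core outcome domains can feasibly be measured. The number of participants who could be asked about itch is itself a feasibility result, and imputing the rest would hide it. The itch effect size is also one of those meant to inform a possible confirmatory trial.

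**Working it through.** The plan states no figure for the itch analysis, so there is nothing to reproduce. The check compares the texts, follows the missing-data rule through, and gives an illustrative count.

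**1. The texts side by side.** For MMSE 24 or higher, all four places agree that itch is asked, although SAP 4.4 adds that IAD must be present. Below 24, protocol 4.1.3 says it is not asked, protocol 2.7.3 and Table 2 imply that it is, and SAP 4.4 says that it is, beside an instrument that protocol Table 2 and 2.7.3 define for pain. The protocol therefore contradicts itself, and the SAP agrees with one side of it.

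**2. The imputation rule if protocol 4.1.3 was followed.** Let R = 1 if itch is recorded at a visit with IAD.
- For MMSE < 24, P(R = 1) = 0 whatever the true itch status.
- Missingness then depends only on MMSE, which is recorded at Day 0. That would ordinarily be classed as MAR, so the SAP 5.1 condition does not stop the imputation.
- With no itch observed below 24, the relation between itch and the other variables in that stratum cannot be estimated. Imputed values there come from the model fitted at MMSE 24 or higher.

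**3. Number of participants affected.** Inputs:
- 220 recruited (SAP section 3).
- Share with IAD 35.4%. This is the prevalence cited in protocol 1.1, used here as an assumption for the share who could have an itch value.
- Share with MMSE below 24: not in the documents; assumed 40% to 80%.

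Formula: 220 × IAD share × share below 24.
- 220 × 0.354 × 0.40 = 31.2, about 31.
- 220 × 0.354 × 0.80 = 62.3, about 62.

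**4. Per arm, with the planned 70 and a wider assumed share of 30% to 90%.**
- With IAD: 70 × 0.354 = 24.8, about 25.
- Of these, below 24: 24.8 × 0.30 = 7.4 to 24.8 × 0.90 = 22.3.
- At 24 or higher: 24.8 × 0.70 = 17.3 down to 24.8 × 0.10 = 2.5.

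Over that range, the group on which the documents disagree runs from under a third to nine tenths of the participants who could have an itch value.

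**The case against.** The strongest reply is that the SAP follows the two places in the protocol that define the outcome and departs only from one summary sentence in 4.1.3. That sentence is itself loose: it also limits pain questionnaires to MMSE 24 or higher, without mentioning that pain below 24 is rated with PAINAD-G. This stands. A reader might infer that the protocol uniformly restricts itch and the SAP overrides it; protocol 2.7.3 and Table 2 do not support that.

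A reader might also infer that the itch model must rest either on invalid self-reports or on imputed values. The documents do not establish this.
- A third course is open: code -2 is left out of the model. The variable table earmarks companion fields for analysing missing itch, imputation is conditional on MAR or MCAR, and a complete-case analysis is planned. None of these, however, says that itch not asked because of MMSE is exempt from imputation.
- Nothing in the documents shows that a yes/no itch answer is invalid below 24. That range includes mild (19 to 23) and moderate (10 to 18) as well as severe impairment.

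Two larger numbers are tempting and should not be used.
- Applying the assumed 40% to 80% to all 220 gives 88 to 176, but itch applies only where IAD is present.
- One could suppose that 60% are impaired and report half of their true itch, turning 40% vs 20% into 28% vs 14%. None of these inputs has a source in the documents. On the odds ratio scale, natural for the planned logistic model, they move the estimate only from (0.40/0.60)/(0.20/0.80) = 2.67 to (0.28/0.72)/(0.14/0.86) = 2.39.

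Finally, itch is a secondary outcome in an exploratory trial without confirmatory tests. That limits the weight of the point but does not remove it.

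**Conclusion.** The concern holds as an unresolved conflict over who is asked about itch, together with a gap in the imputation rule. If protocol 4.1.3 governed data collection, SAP 5.1 as written would allow itch to be imputed in a stratum with no observed itch. If protocol 2.7.3 and SAP 4.4 governed, self-reports from all MMSE levels enter one model with no separate view of the impaired group. If code -2 is silently dropped, the result describes MMSE 24 or higher only, and the SAP does not say so. The documents do not show which of these applies.

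The illustrative size is about 31 to 62 of 220 participants. It rests on the assumed 35.4% with IAD and the assumed 40% to 80% below MMSE 24. No size or direction of bias in the itch effect can be derived from the documents.

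**What to change.** - **Reconcile** protocol 4.1.3, protocol 2.7.3, protocol Table 2 and SAP 4.4 with how itch was actually collected, and record the outcome in the SAP.
- **SAP 4.4:** remove itch from the PAINAD-G line.
- **SAP 5.1:** state that itch coded -2 because it was not asked owing to MMSE below 24 is missing by design and is not imputed.
- **SAP 7.2:** report the itch model for MMSE 24 or higher and, if answers exist below 24, also for all respondents. Show itch rates by MMSE band and arm, and state the denominator for each.

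Reporting both populations avoids discarding collected answers on a core symptom; restricting the only itch model to MMSE 24 or higher would be a trade-off that the documents do not settle. The changes are to SAP wording and one descriptive table. The cost is a smaller denominator and a wider interval for itch.

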4.4.1 Safety/Tolerability

Events are defined according to the definition of the EU regulation 2017/745 Medical Device Regulation (MDR) Article 2 and will be checked regularly.

Adverse events

- Untoward medical occurrence, e.g. allergic reaction
- Unintended disease or injury
- Untoward clinical signs, e.g.: abnormal laboratory finding

Incidents

- any malfunction or deterioration in the characteristics or performance of the skin protectants

Serious adverse events / Serious incidents that (in-)directly lead to

- Death
- Serious deterioration in the health

4.4.2 Quality of life

There is no specific questionnaire for quality of life assessment.

4.4.3 Feasibility and adherence

Feasibility and adherence relevant outcomes are evaluated by analysing the available diaries for the study. Due to the nature of the diaries, they will be evaluated separately by an unblinded person of the study team to ensure the blindedness of the statistician for further analyses.

Characteristic		Type	Scale	Comment/Analysis
Feasibility	Diary			
-	-	-	-	Assessment not possible
Adherence	Diary			
Percentage of completely/ correctly documented days:		Numeric	xx [%]	
Count diary_00x1 per patient x...# of day (opt.: divide by days under study)
 
Each diary day includes several variables (e.g. count of urinary incontinence episodes, count of stool incontinence episodes, change of incontinence material, product application, etc.). A day is defined as follows:
 
 • Correctly documented: All fields are fully completed (100% documented). • Partially correct: One or more fields are missing. • Not filled: Only the date is recorded and all other entries are missing. 
Note: A "missing" entry indicates that data was not provided, while a deliberate zero indicates that the event did not occur.

Number of product applications		Numeric	Xx [quantity]	
Summarize diary_00x6y per patient, per day and week x...# of day y...letter of application on day x

5 Handling of missing values and outliers

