Outcomes	
 IAD incidence Erythema Erosion Maceration IAD-related pain IAD-related itch Satisfaction with treatment Willingness to participate Retention Adherence to prescribed intervention Adverse Events (AEs) and Serious Adverse Events (SAEs) according to the definition of the EU regulation 2017/745 Medical Device Regulation (MDR) Article 2 (57) and (58) Incidents and Serious Incidents according to the definition of the EU regulation 2017/745 MDR Article 2 (64) and (65)

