4. Procedures	After regular skin cleansing in the morning, the skin protectant is applied to dry skin.	After regular skin cleansing in the morning and evening, the skin protectant is applied to dry skin. In addition, the product is reapplied following the skin cleansing after a stool incontinence episode.	After regular skin cleansing, no additional skin protectant is applied.
	Prior to the beginning of the study, ward nurses are educated in interactive face-to-face meetings. Handouts will be provided and posters summarizing the study procedures are placed on the wards. Regular refresher meetings are held every three months under the supervision of the investigators.		

5. Who provides?	Ward nurses who participated in an educational session about this study and the procedures and thus have study-relevant knowledge.		
6. How	
 - After removal of the incontinence briefs, the skin is cleansed and dried. - An oil may be used to remove stool and/or residual products. - The skin protectant is applied to dry skin. According to manufacturer instructions, the spray must be hold approximately 10 cm away from the skin surface. A uniform layer of the product is applied using a sweeping motion over the area to be protected. The film must be completely dry before the person is turned onto their back, new incontinence materials are placed or clothing is put on. - New incontinence pants are put on (if needed from the view of the nurses). 	
 - After removal of the incontinence briefs, the skin is cleansed and dried. - An oil may be used to remove stool and/or residual products. - The skin protectant is applied to dry skin. - New incontinence pants are put on (if needed from the view of the nurses). 	
 - After removal of the incontinence briefs, the skin is cleansed and dried. - An oil may be used to remove stool and/or residual products. - New incontinence pants are put on (if needed from the view of the nurses).
7. Where	In the patient rooms, in or outside of the bed.		

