1.1.2 Secondary objectives

Additional objectives are to test the feasibility of conducting a confirmatory RCT to prevent IAD and to evaluate the feasibility of measuring the Core Outcome Domains for IAD trials.

The trial will answer the following research questions:

- What are the effect sizes of the outcomes when comparing the intervention groups and the control group?
- Is the implementation of a standardized skin protection regime for the prevention of IAD feasible in geriatric hospital wards and nursing homes?
- Does the implementation of a standardized skin protection regime for the prevention of IAD reduce IAD-related itch and IAD-related pain?
- Is the measurement of Core Outcome Domains for IAD trials feasible?

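### SAP 4.4.3 never compares adherence with the arm-specific application schedule, and the SAP text names no estimate for retention or core-outcome completeness

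*Combined protocol and SAP*

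**What the plan says.** **Objectives and outcomes.** SAP 1.1.2 states: "Additional objectives are to test the feasibility of conducting a confirmatory RCT to prevent IAD". Two of its four research questions are about feasibility: "Is the implementation of a standardized skin protection regime for the prevention of IAD feasible in geriatric hospital wards and nursing homes" and "Is the measurement of Core Outcome Domains for IAD trials feasible". The outcome list in the protocol Summary contains three neighbouring items: "Willingness to participate Retention Adherence to prescribed intervention".

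**Adherence.** SAP 4.4.3 has two rows, both carried forward from protocol Table 2.
- The first is a percentage of diary days. A day is counted under "Correctly documented: All fields are fully completed (100% documented". A zero entered on purpose is a valid entry. Division by days under study is marked as optional.
- The second sums product applications per patient, per day and per week.

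**Feasibility.** The row in SAP 4.4.3 reads "Assessment not possible". The SAP file history gives the reason: the share of eligible people willing to take part could not be determined.

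**Prescribed schedule.** Protocol Table 1 (items 4, 8 and 9) sets one application a day in arm 1 and none in the control arm. Arm 2 has two a day, and Table 1 says further: "In addition, the product is reapplied following the skin cleansing after a stool incontinence episode". The protocol Summary, protocol 2.3 and the SAP synopsis describe arm 2 only as a daily application.

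**The concern.** The listed outcome is adherence to what was prescribed, so the prescribed amount is the natural denominator. Neither row uses it. The first row describes how well the diary was kept. The second cannot be compared across arms, because the required number differs by arm and, within arm 2, depends on stool episodes.

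The feasibility questions also remain in the SAP without a quantity that answers them. The one item that could not be assessed was willingness to participate. Retention and the completeness of core-outcome measurement are separate matters, and the variables for both are collected.

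At stake is what the trial can hand to the planners of a confirmatory trial: how much of each regime was delivered, how many participants stayed to Day 14, and how often each core outcome could be obtained.

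**Working it through.** No sample size, power or event figure is involved, so there is no stated figure to reproduce. The check traces objective, outcome, variable and analysis, and then works one example.

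**1. Required applications over the 14-day intervention (protocol Table 1)**

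| Arm | Rule | Over 14 days |
|---|---|---|
| 1 | 1 per day | 14 × 1 = 14 |
| 2, no stool-triggered reapplication | 2 per day | 14 × 2 = 28 |
| 2, assumed 1 reapplication per day | 3 per day | 14 × 3 = 42 |
| 2, assumed 2 reapplications per day | 4 per day | 14 × 4 = 56 |
| Control | 0 | 0 |

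The stool rates are assumptions; the documents give none.

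**2. One arm 2 participant: 14 applications recorded, all diary fields filled on 14 days**
- SAP row 1: 14/14 = 100% of days documented.
- SAP row 2: 14 applications, or 1 per day.
- Recorded over required under Table 1: 14/28 = 50% at most, and 14/42 = 33% at one reapplication per day.
- If the word daily were read as once a day: 14/14 = 100%.

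The last two lines show why the passages on arm 2 must be reconciled before a denominator is fixed. A count of 14 is full delivery in arm 1 and at most half in arm 2 under Table 1.

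**3. The optional denominator.** A participant who leaves after 7 fully documented days can appear as a count of 7, as 7/7 = 100% of days under study, or as 7/14 = 50% of the planned period.

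**4. Are the data there?**

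| Quantity | Variables described as collected | Estimate named in the SAP text |
|---|---|---|
| Applications and stool episodes | diary fields, diary_00x6y (SAP 4.4.3) | count only, no ratio |
| Retention to Day 14 | sc_0021, reasons sc_0031 to sc_0038 (SAP 4.1) | none |
| Visits performed | visit_0011, reason visit_0013 (SAP 4.1) | none |
| Core outcomes obtained | no-assessment codes and check variables for pain, itch, satisfaction and erythema level (SAP 4.2) | none |

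SAP section 7 and the example table layouts add no adherence, retention or completeness analysis. The layouts are only exemplary, so their silence is weak evidence.

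**5. Precision that a retention table would give.** The plan enrols 70 per arm to analyse 60. If 60/70 = 85.7% were retained in an arm, the Wilson 95% interval would be 75.7% to 92.1%. At an assumed 70% it would be 58.5% to 79.5%, and at 95% it would be 87.2% to 98.2%.

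**The case against.** The case for leaving the SAP alone has real content.

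- **Both adherence rows are prespecified.** They follow protocol Table 2, and the SAP is dated after recruitment. This stands as a reason to add a measure and label it as added. It is not a reason to omit it.
- **The Feasibility row was narrow from the start.** In protocol Table 2 it held only willingness to participate and reasons for declining. A reader might infer that the SAP struck out feasibility as a whole. It did not; it emptied one row for one stated reason. What remains is that the two feasibility questions have no other endpoint attached.
- **Indirect evidence is planned.** It consists of ITT against per-protocol results, exclusion reasons per group, completion variables, a participant flow chart and 12 interviews. A reader might infer that the feasibility objective goes unanswered; that is too strong. The flow chart is not visible in the text version and may show part of retention.
- **Full marks with no product.** A reader might infer that adherence could be reported as 100% when nothing was applied. The adjacent count would show zero. A participant given no treatment leaves the full analysis set, and a gap above 72 hours leads to per-protocol exclusion.
- **Control arm.** A reader might infer that the count is blind to control participants given a protectant. Diaries record leave-on products, and SAP 4.4.3 does not restrict the count by arm.
- **Adherence against efficacy.** A reader might infer that low adherence could not be separated from lack of effect. The per-protocol analysis addresses this in part. It is coarse: one application a day never produces a 72-hour gap, and the SAP does not say whether it would count as incorrect application.

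**Conclusion.** The point holds as a gap in measurement. Neither adherence row is compared with the arm-specific schedule. The only percentage describes diary completion, and its denominator is optional. The SAP text names no estimate for retention or core-outcome completeness, although the feasibility questions are kept.

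The size is shown by the arm 2 example: 100% documented against at most 50% of the Table 1 schedule. This assumes that Table 1 governs, a 14-day intervention period, and that no stool-triggered reapplication could lower the required number below 28.

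This is a worthwhile, inexpensive improvement to an exploratory trial. It does not affect the efficacy estimates. Willingness to participate stays unassessable; diary, visit and completion data cannot replace it.

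**What to change.** 1. **Reconcile first.** Bring the passages that describe arm 2 as daily into line with Table 1. State how an episode cleaned at scheduled morning or evening care is counted, since Table 1 ties reapplication to an episode in one item and to stool removal in another.
2. **Keep both rows.** Relabel the first as diary completeness and always divide it by days under study.
3. **Add adherence to the prescribed intervention.** For each participant, divide recorded applications (diary_00x6y) by the number that the intervention description requires, using diary stool counts where reapplication applies. Summarise by arm with a 95% CI. The required number in the control arm is zero, so report instead the share of control days with any protectant recorded.
4. **Limit the not-possible entry** to willingness to participate.
5. **Add feasibility tables by arm and setting.**
   - Retention to Day 14 (sc_0021, sc_0031 to sc_0038), among randomised participants. The SAP notes that the No code may include screening failures, and one of the Yes codes is completion before the Day 14 visit.
   - Visits performed (visit_0011).
   - Percentage of planned assessments obtained per core outcome. Count a pain or itch assessment as planned only where IAD is present, and a satisfaction assessment only where MMSE is 24 or higher, as in SAP 4.4.

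The hospital setting has 25 participants, about 25/3 ≈ 8 per arm, so show counts beside percentages there.

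**Cost.** The change needs SAP wording, a counting rule for arm 2 and a few descriptive tables, labelled as added to the prespecified measures. The diary tables fall to the unblinded evaluator whom SAP 4.4.3 already provides for, so the statistician stays blinded. No new data are needed.
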